3. OBJECTIVES

Objectives:

Primary objective:

Assessment of arthralgia scores and patients` compliance within the first year of anastrozole treatment¹, stratified by upfront and switch therapy as well as assessment of the relationship between compliance and arthralgia scores.

Secondary objectives

Incidence of arthralgias and arthralgia characteristics within the first year of anastrozole therapy¹ stratified by upfront and switch therapy and assessment of the relationship of arthralgia incidence and arthralgia characteristics to patients` compliance.

Retrospective assessment of incidence of pre-existing arthralgias before start of anastrozole treatment, stratified by upfront and switch therapy.

Descriptive assessment of arthralgia therapy and of costs of arthralgia therapy, stratified by upfront and switch therapy.

The assessment of compliance and of arthralgia therapy will be compared to and validated by the corresponding data obtained by the sick funds of the patients.²

Assessment of subjective perception of side-effects by the patients, stratified by upfront and switch therapy.

Identification of factors influencing and correlating to treatment-emergent arthralgias, such as patient's characteristics (e.g. age, BMI), disease characteristics, duration of anastrozole treatment, subjective perception of side-effects by the patients etc.

Identification of factors influencing and correlating to patients' compliance; for example patient's characteristics (age), disease characteristics, concomitant medication, subjective perception of side-effects by the patients, incidence and characteristics of arthralgias (time between start of anastrozole therapy and occurrence, intensity and duration of arthralgias), incidence of AEs etc.

Compare time to progression (TTP) between patients with arthralgias and patients without arthralgias in the first year of anastrozole treatment, stratified by upfront and switch therapy.

Assessment of safety and tolerability of anastrozole.

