The ITT analysis set will be used for the primary analysis of compliance and arthralgia scores. The safety population(s) will be the basis for the analysis of costs and safety analyses and for a secondary analysis of arthralgia scores. Additionally, all women who completed this NIS and who were compliant according to the criteria defined in the protocol for the total duration of 12 months of anastrozole treatment will be analysed separately with regard to the arthralgia characteristics (VAS score, incidence, intensity etc), side-effect management, related costs, perception of side effects etc.

Demographic data and all other important baseline characteristics will be presented for both, the ITT and safety analysis sets. The results will be presented in a descriptive manner.

Other analysis sets may be defined.

¹ The start of the adjuvant treatment with anastrozole is defined by the date of the first tablet intake. If this date is not assessible, the date of the first prescription of anastrozole can be used instead.

² This is only applicable to patients who consented to data transfer and who are insured by sick funds who joined the respective contract. Data transferred from the sick funds will include breast-cancer related costs from 12 months before study start up to the end of the study for the respective patient.

Outcome variables

Compliance:

Compliance is defined by the percentage number of patients being 'compliant' to anastrozole therapy, based on the following information collected by the doctor at 0, 3, 6 and 9 months after study start:

1) Question about the daily intake of anastrozole (to be answered by the investigator):

”The patient was instructed to take 1 anastrozole tablet per day. However, it’s still possible that the intake has sometimes been forgotten. How many tablets, according to your impression of the patient, has the patient actually taken during the last year?”

Scoring:	0 – none	0%
	1 – few	[0% ; 20%]
	2 – less than half	[20% ; 40%]
	3 – approximately half	[40% ; 60%]
	4 – more than half	[60% ; 80%]
	5 – almost all	[80% ; 100%]
	6 – all	100%.

2) Question about the daily intake of anastrozole (to be answered by the patient in the patient questionnaire)

”You were instructed to take 1 anastrozole tablet per day. However, it’s still possible that the intake has sometimes been forgotten. How many tablets have you actually taken during the last year?”

Scoring:	0 – none	0%
	1 – few	[0% ; 20%]
	2 – less than half	[20% ; 40%]

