6. PATIENT SELECTION AND PLANNED NUMBER OF PATIENTS

Patients are eligible for inclusion in this NIS if they have taken anastrozole either upfront or following two to three years of tamoxifen treatment (“switch”) for at least three and not more than six months prior to offering an individual participation in this program. Treatment should follow local therapy guidelines and standard practice. Treatment decisions for patients participating in this study including assessments or supportive therapy during follow-up visits will also follow guidelines and remain independent of the program.

The patient population will include postmenopausal women with hormone-receptor positive primary breast cancer scheduled for adjuvant upfront endocrine treatment with anastrozole or following two to three years of tamoxifen treatment (“switch”) according to the current SmPC (Appendix C). Patients will have taken anastrozole for at least three months and not more than six months before the start of the study.

It is planned to enrol and document 3212 patients in this NIS. Further details regarding the objectives and the sample size consideration can be found in Section 3 and 11.5..

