7. PROGRAM PLAN AND PROCEDURES

7.1 Overall design and flow chart

This is an open, multicentre NIS.

[figure not shown]
It is planned to enrol subjects into this NIS between Q1 2009 and Q1 2010. Based on the plan outlined below, it is assumed that the last subject will be enrolled in Q1 2010 and subsequently documented until Q4 2010.

The treatment with anastrozole can be stopped at any time.

Furthermore it is expected, that the last completed eCRF will be filled in Q4 2010. It is planned to close all centres until end of Q1 2011 (i.e. the fees for all participating centres are paid).

Treatment with Anastrozole

Study duration

*or at point of treatment discontinuation

Evaluation period

Information to patients: study start, weeks 1, 3, 5, 8, 12, 20

- 1 The start of the adjuvant treatment with anastrozole is defined by the date of the first tablet intake. If this date is not available, the date of first prescription will be taken.
- 2 The end of participation in this NIS is defined as recurrence or death or withdrawal of informed consent is documented via WBDC. Patients who stop endocrine therapy (i.e. do not take further treatment) or patients who switch to an adjuvant endocrine therapy with tamoxifen or a different aromatase inhibitor or patients considered 'lost to follow-up' (i.e.: can no longer be contacted) will be documented as premature terminations. Otherwise this NIS terminates after completion of 12 (15) months observation period (12 respectively 15 months observation period results from time slot for inclusion, minimum 3 and maximum 6 months of anastrozole therapy prior to enrolment)

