8.1.1 Documentation at registration

The following data should be documented at registration/enrolment

Demographics	Year of birth
Patient number	
Patient insured in a sick fund part of GWQ?	Yes; no
Informed consent	
Inclusion / exclusion criteria	
Was the patient identified for anastrozole therapy 1mg / day?	Yes; no
Date of the 1 st prescription	
Start date of anastrozole therapy	
Breast centre that performed surgery	Name Address
Investigator details	Fax number E-mail address Name

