8.2.2 Documentation at 3, 6 an 9 months after study start

The following data should be documented after 3, 6 and 9 months after study start or at the time point of treatment discontinuation

Demographics	Year of birth
Observation interval	Date of assessment
Demographics	Year of birth

Observation interval	Date of assessment
Medication intake	
Daily intake of drugs/tablets apart from the prescribed anti-cancer agent?
 
Number of drugs and tablets per day? (none, unknown)
 
Self reported medication intake (questions from reference): Do you occasionally forget taking of your medicine ? (yes,

	
no)
 
Are you occasionally neglectful concerning your medicine intake? (yes, no)
 
When you feel better, do you occasionally stop taking your medicine? (yes, no)
 
Sometimes when you feel worse, do you stop taking your medicine? (yes, no)
 
How do you feel about taking your medication?
 
 - never mind - don't like it 
Why don't you like taking your medication?
 
 - difficulties in swallowing tablets - disturbs my daily routine - reminds me of my disease - other 
Compliance to anastrozole: You were supposed to take one tablet anastrozole per day. However, daily medication intake may be forgotten. How many anastrozole tablets did you actually take from the start of anastrozole therapy until today:
 
 - none - few - less than half - almost the half - more than half - almost all - all

Questions on arthralgia occurrence, characteristics and management
	
Did you experience any arthralgias during the past three months? (yes, no)
 
Did the arthralgia intensity change during the past three months? (yes, the intensity decreased; yes, the intensity increased; no)
 
Which medication did you take because of arthralgias?
 
Did you consult any doctor because of arthralgias, and in which field did the doctor specify? (general practitioner, number of times; internist, number of times; orthopedist, number of times; rheumatologist, number of times; pain

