11.4.1 Outcome variables

The objectives outlined in chapter 3 will be analysed as follows:

Primary objective:

Assessment of arthralgia scores and patients' compliance within the first year of anastrozole treatment¹, stratified by upfront and switch therapy as well as assessment of the relationship between compliance and arthralgia scores.

The absolute number and percentage of compliant patients will be calculated. Groups will be compared with Fisher's exact test

From the arthralgia scores an overall score will be calculated (sum of 14 single item scores divided by 14). Groups will be compared using t-test.

Relationship between compliance and arthralgia scores will be assessed using logistic regression analysis.

Of primary interest are the 3 months data (data obtained within the first three months of anastrozole therapy). Secondly, the other time points will be evaluated.

Secondary objectives:

Incidence of arthralgias and arthralgia characteristics within the first year of anastrozole therapy¹ stratified by upfront and switch therapy and assessment of the relationship of arthralgia incidence and arthralgia characteristics to patients' compliance.

The absolute number and percentage of patients with at least one event of arthralgia within pre-defined intervals (0-3, 3-6, 6-9, 9-12 and 12+ months after the start of anastrozole treatment) will be calculated.

Characteristics of arthralgias within each time interval will be evaluated descriptively stratified by upfront and switch therapy:

- Maximum intensity, localization, relationship to study drug, diagnostics and arthralgia management presenting number and percentage of each category.
- Time between start of anastrozole therapy and first incidence of arthralgia will be analysed using the Kaplan-Meier method.

Maximum duration of arthralgias will be evaluated descriptively, presenting standard statistics.

Retrospective assessment of incidence of pre-existing arthralgias before start of anastrozole treatment, stratified by upfront and switch therapy.

The absolute and percentage number of patients with pre-existing arthralgias will be calculated stratified by upfront and switch therapy.

Descriptive assessment of arthralgia therapy and of costs of arthralgia therapy, stratified by upfront and switch therapy.

Evaluation will be performed descriptively with standard statistics and associated with cost modules of sick funds.

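### Compliance and the arthralgia score are collected by months since study start while the primary objective runs on treatment time, so each visit mixes women up to three months apart on drug and the last score falls after the first year

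*Protocol*

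**What the plan says.** - **Target period.** Section 3 sets the primary objective as arthralgia scores and "compliance within the first year of anastrozole treatment". A footnote starts that clock at the first tablet, or at the first prescription if the tablet date is unavailable.
- **Entry.** Section 6: "Patients will have taken anastrozole for at least three months and not more than six months before the start of the study".
- **Collection.** Section 3 makes compliance "based on the following information collected by the doctor at 0, 3, 6 and 9 months after study start". For the patient questionnaire, which carries the patient's compliance answer and the VAS items, section 8.2.2 says: "The following data should be documented after 3, 6 and 9 months after study start or at the time point of treatment discontinuation".
- **End of observation.** Section 7.1 acknowledges the span: "12 respectively 15 months observation period results from time slot for inclusion, minimum 3 and maximum 6 months of anastrozole therapy prior to enrolment".
- **Analysis.** Section 11.4.1 compares groups on compliance with Fisher's exact test and on the mean of the 14 items with a t-test, and relates the two outcomes by logistic regression. None of these carries a term for time on treatment. The 3-month data come first, described as coming from the opening three months on anastrozole; then "Secondly, the other time points will be evaluated".
- **Other clocks.** Section 11 places the first analysis after at least three months of observation, and section 11.3 defines the ITT set by the first three months from study start. Sections 11.2 and 11.4.1 assign arthralgia occurrences to intervals from treatment start, with a separate interval after month 12.
- **Data available.** Section 8.1.1 records "Start date of anastrozole therapy" for each woman at registration.

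**The concern.** The objective is stated on one clock and the two co-primary outcomes are gathered on another, with a variable offset of 3 to 6 months between them. A table labelled by study visit does not describe a fixed point in treatment, and its last column does not describe the first year. The primary time point is itself defined on both clocks, so two analysts following the text could report different primary results. If upfront and switch patients entered at different times on average, part of any difference between them at a visit could reflect time on drug. The same applies to the compliance–arthralgia relation if both outcomes change with treatment time.

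**Working it through.** **Stated sample sizes.** 44% against 50%, two-sided 5%, 80% power, continuity-corrected: 1119 per group, as in section 11.5. Difference 0.4 with SD 2, t-test: 393.4, rounded up to 394, as stated. For 30% drop-out, 2 × 1119 / 0.70 gives 3198, against 3212 stated (0.4% apart). The point here does not alter these figures.

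**Visit times.** Treatment month = study month + entry time, with entry between 3 and 6.

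| Study month | Treatment months |
|---|---|
| 0 | 3–6 |
| 3 | 6–9 |
| 6 | 9–12 |
| 9 | 12–15 |

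The spread is 6 − 3 = 3 months at every visit. At study month 9 only a woman who entered at exactly month 3 is still at the 12-month mark.

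**Primary time point.** The earliest visit is at treatment month 3–6. Only a woman entering at exactly month 3 can supply a rating at the end of the opening three months. The visit three months after study start lies at treatment months 6–9. The time reference in section 11.4.1 therefore cannot be met under the entry rule, and it differs from sections 11 and 11.3.

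**What a month-9 compliance answer covers.**
- Questionnaire wording (from start of therapy to the day of answering): 12 of 12 to 12 of 15 months fall in the first year, that is 100% to 80%.
- Section 3 wording (the last year): 12 of 12 to 9 of 12 months, that is 100% to 75%.
- The doctor's item in section 8.1.3 refers to the observed period, which is not defined further.

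The VAS recall period is in appendices not at hand. I assume the score describes the patient's state around the day of rating.

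**Illustration of group bias in compliance.** Inputs: section 11.5 (fall to about 50% in the first year; 6 points relevant) and section 1.3 (23% non-compliant after one year on tamoxifen, so 77%). My assumptions are a straight line from 100% and a rating that follows it. The slopes are (100 − 50)/12 = 4.17 and (100 − 77)/12 = 1.92 points per month. Spurious difference = slope × difference in mean entry time. The rejection rate uses a normal-approximation two-proportion test, pooled variance under the null, no continuity correction, 1119 per group, proportions centred on 50% or 77%, and no true difference.

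| Entry difference (months) | Points, 50% case | Rejection | Points, 77% case | Rejection |
|---|---|---|---|---|
| 0 | 0 | 5.0% | 0 | 5.0% |
| 0.5 | 2.08 | 16.6% | 0.96 | 8.4% |
| 1 | 4.17 | 50.5% | 1.92 | 19.0% |
| 1.5 | 6.25 | 84.1% | 2.88 | 36.6% |
| 3 (maximum) | 12.5 | 100% | 5.75 | 89.9% |

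Six points need 6/4.17 = 1.44 months in the 50% case. In the 77% case they would need 3.13 months, more than the entry window allows. The protocol gives no time course for the arthralgia score, so no comparable figure can be set for it.

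**The case against.** - **The analysis clock is inferred.** The visit schedule is a collection schedule; the objective's footnote and the time reference in section 11.4.1 both point to the first tablet. This stands in part: the protocol does not say outright that the tests run by study visit. But sections 11 and 11.3 count from observation or study start, and the treatment-clock reference cannot be met.
- **Month 9 is secondary and the 12-to-15-month span is disclosed.** True, and it limits the weight of the labelling point. The three-month mix affects every visit.
- **Compliance questions look back.** This stands. A reader might infer that month-9 compliance is not first-year data; the patient item and the section 3 wording do not support that.
- **Bias between upfront and switch is hypothetical.** This stands. A reader might infer that the comparison is biased, or the compliance–arthralgia relation confounded. The protocol reports no difference in entry times and no time course for the score, and equal mean entry times remove the group bias shown in the illustration.
- **Treatment duration is already handled.** It is named in the secondary regression for arthralgia, and compliance factors are to be analysed likewise. It is absent from the primary comparisons.
- **Windows and covariates belong in the SAP, and p-values are exploratory.** Fair for detail. The conflicting definition of the primary time point, however, is fixed in the protocol, and an exploratory p-value does not correct a mislabelled estimate.

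**Conclusion.** The point holds as a mismatch of clocks. By the protocol's own dates, each visit spans three months of treatment time, and the month-9 arthralgia score lies beyond the first year for nearly all women (given the assumption on VAS recall). The 3-month time point that carries the primary analysis is described in a way the entry rule practically rules out, and differently elsewhere. It does not follow that the upfront/switch contrast is biased. That needs unequal mean entry times; under the assumed straight lines each month of imbalance would give about 4.2 points (50% case) or 1.9 points (77% case, at most 5.75). Because the compliance items cover a long period, real ratings may respond less than these lines suggest. The change is worth making because the required date is already collected.

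**What to change.** In section 11.4.1:

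1. Compute months since first tablet (first prescription as the existing fallback) at each compliance and VAS rating. Assign ratings to treatment windows 3–6, 6–9, 9–12 and 12+ months, or adjust the group comparisons and the compliance–arthralgia regression for treatment month at the rating. When visits run on schedule these windows coincide with the visits: they correct the label and catch off-schedule ratings, but only the adjustment removes the three-month mix.
2. Limit first-year statements on the VAS score to ratings up to treatment month 12, and label later ones as beyond the first year.
3. Reconcile the 3-month definition with sections 11 and 11.3 and with the entry rule in section 6, so that one clock and one visit define the primary data.

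Cost: wording and a few model lines. No new data are needed and the sample size is unchanged. The downside is that by-visit tables become secondary.

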4. PRODUCT-SPECIFIC INFORMATION ON ANASTROZOLE

Anastrozole has been approved in Germany (Arimidex[®]). The current summary of product characteristic (SmPC, "Fachinformation") can be found in Appendix C of this observational plan.

Anastrozole is contraindicated for patients with severe renal function disorders (Creatinine clearance < 20 ml/min) or with moderate or severe disorders of hepatic function.

5. CENTRE SELECTION AND PLANNED NUMBER OF CENTRES

This NIS study is a non-interventional, multi-centre, observational study with approximately 700 specialised clinics and office based gynaecologists or oncologists. Study Centres will be selected in concern of the criteria of the medical experiences and the knowledge of the disease of study investigators.

6. PATIENT SELECTION AND PLANNED NUMBER OF PATIENTS

Patients are eligible for inclusion in this NIS if they have taken anastrozole either upfront or following two to three years of tamoxifen treatment (“switch”) for at least three and not more than six months prior to offering an individual participation in this program. Treatment should follow local therapy guidelines and standard practice. Treatment decisions for patients participating in this study including assessments or supportive therapy during follow-up visits will also follow guidelines and remain independent of the program.

The patient population will include postmenopausal women with hormone-receptor positive primary breast cancer scheduled for adjuvant upfront endocrine treatment with anastrozole or following two to three years of tamoxifen treatment (“switch”) according to the current SmPC (Appendix C). Patients will have taken anastrozole for at least three months and not more than six months before the start of the study.

It is planned to enrol and document 3212 patients in this NIS. Further details regarding the objectives and the sample size consideration can be found in Section 3 and 11.5..

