The patient population will include postmenopausal women with hormone-receptor positive primary breast cancer receiving adjuvant endocrine treatment with anastrozole upfront or following two to three years of tamoxifen therapy (“switch”) according to the current SmPC (Appendix C). Patients will have received anastrozole treatment for at least 3 months and up to 6 months before the start of the study.

Randomisation

- No randomisation will be performed in this study.

Outcome variables

Compliance:

Compliance is defined by the percentage number of patients being ‘compliant’ to anastrozole therapy, based on the following information collected by the doctor at 0, 3, 6 and 9 months after study start:

- 1) Question about the daily intake of anastrozole (to be answered by the investigator):

”The patient was instructed to take 1 anastrozole tablet per day. However, it’s still possible that the intake has sometimes been forgotten. How many tablets, according to your impression of the patient, has the patient actually taken during the last year?”

Scoring:	0 – none	0%
	1 – few	[0% ; 20%]

2 – less than half	[20% ; 40%]
3 – approximately half	[40% ; 60%]
4 – more than half	[60% ; 80%]
5 – almost all	[80% ; 100%]
6 – all	100%.

- 2) Question about the daily intake of anastrozole (to be answered by the patient in the patient questionnaire)

”You were instructed to take 1 anastrozole tablet per day. However, it’s still possible that the intake has sometimes been forgotten. How many tablets have you actually taken during the last year?”

Scoring:

0 – none	0%
1 – few	[0% ; 20%]
2 – less than half	[20% ; 40%]
3 – approximately half	[40% ; 60%]
4 – more than half	[60% ; 80%]
5 – almost all	[80% ; 100%]
6 – all	100%.

- 3) A patient will only be defined as being ‘compliant’ when the answer of the doctor **and** the patient score ‘5’ or ‘6’ concerning the question regarding the number of tablets actually taken.

Arthralgias

Arthralgias will be summarized by incidence, localization, onset, duration, intensity, and relationship to study drug, diagnostics and arthralgia management (e.g. medication, physiotherapy, doctor’s visits, change of life style etc.). Arthralgia characteristics will be particularly assessed using VAS scores (Appendices E and F).

Perception of side-effects

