6.1 Inclusion and exclusion criteria

Based on the current version of the SmPC for anastrozole patients participating in this study must meet all of the following criteria:

1. Provision of Written Informed Consent
2. Postmenopausal women aged 18 years or older;
Postmenopause is defined as
 - Natural menopause with menses >1 year ago or
 - Serum FSH (> 20 IU/ l), and E2 levels in the postmenopausal range or
 - patients who had bilateral oophrectomy
3. Histologically / cytologically confirmed primary diagnosis of early breast cancer (M0) with hormone sensitive tumour (ER+ve and/or PgR+ve)
4. Patients, who underwent breast cancer surgery and, if applicable, radiation therapy and/ or neo/adjuvant chemotherapy and have taken adjuvant endocrine treatment with anastrozole (upfront or following two to three years of tamoxifen treatment) for at least 3 month and for a maximum of 6 months
5. Patient is considered suitable for treatment with an oral therapy.
6. Ability to organize the daily intake of drugs
7. Ability to read and understand German

8. In case of a previous therapy with tamoxifen (switch-therapy), duration of tamoxifen treatment for at least two and up to three years.

Any of the following is regarded as a criterion for exclusion from the program:

1. Patients, who are unable to provide written consent
2. Concomitant treatment with drugs known to affect sex hormonal status and Tamoxifen
3. Known hypersensitivity to anastrozole or any excipients of the tablet. The contraindications, warning notices and measures of precaution of this product, as notified in the product information, have to be respected
2. Patients with ductal carcinoma in situ (DCIS) without primary diagnosis of early breast cancer (M0)
3. Evidence of any significant clinical disorder or laboratory finding which in the opinion of the investigator, makes it undesirable for the patient to participate in the program
4. Previous enrolment in the present program
5. Participation in any other clinical trial within 30 days of enrolment
8. Involvement in the planning and conduct of the program (applies to both AstraZeneca staff or staff at a participating site or at the CRO).

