11.5 Justification of sample size

Based on previous data, it can be assumed that a patients’ compliance will decrease to approximately 50% during the first year of antihormone therapy, a difference in patients’ compliance of 6% will be judged clinically relevant. In order to recognize a statistically significant difference of 6% between two groups or between different time points 1119 patients are required per group or time point.

In the following table the sample size which is needed to detect a difference of 6% is presented with the corresponding odds ratios starting with an event rate of 44% for a standard group.

Two group continuity corrected chi-square test of equal proportions (odds ratio = 1) (equal n's, 2-sided test, $\alpha= 0.05$, Power = 80%)

Group 1 proportion, π_1		I
0,44	Proportion, π_2	0,5
	Odds ratio, $\psi = \pi_2 (1 - \pi_1) / [\pi_1 (1 - \pi_2)]$	1,273
	n per group	1119

nQuery Advisor 7.0

In a newly performed study a mean arthralgia score of 4 was found with a standard deviation of 1.86. Assuming a standard deviation (sd) of 2 and a difference of 10% between 2 groups a sample size of 394 in each group will have 80% power to detect a difference in means of - 0,4 (the difference between a Group 1 mean, μ_1 , of 4 and a Group 2 mean, μ_2 of 4,4) assuming that the common standard deviation is 2 using a two group t-test with a 0,050 two-sided significance level.

In the following table the sample size which is needed to detect a difference of 10% in the arthralgia score is shown for the t-test.

Comparison of equal means (2-sided test, $\alpha= 0.05$, Power = 80%)

	t-test
Group 1 mean, μ_1	4,000
Group 2 mean, μ_2	4,400
Difference in means, $\mu_1 - \mu_2$	-0,400
Common standard deviation, σ	2,000
Effect size, $\delta = \mu_1 - \mu_2 / \sigma$	0,200
n per group	394

nQuery Advisor 7.0

Based on previous non-interventional trials, approximately 25 to 40% of the patient documentation will not be accessible. Therefore, assuming a drop-out rate of 30%, 3212 patients will be enrolled to ensure a sufficient number of evaluable patients.

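### Enrolment is open only to women already 3 to 6 months on anastrozole, so the first-year objectives timed from the first tablet describe persisters, not all starters

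*Protocol*

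**What the plan says.** **Who can enter.** Section 6 states: "Patients will have taken anastrozole for at least three months and not more than six months before the start of the study". Inclusion criterion 4 in section 6.1 repeats it, requiring anastrozole "for at least 3 month and for a maximum of 6 months", and the Synopsis has the same window.

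**What is to be estimated.** The primary objective in section 3 covers arthralgia scores and "compliance within the first year of anastrozole treatment", by upfront and switch therapy. The first secondary objective is "Incidence of arthralgias and arthralgia characteristics within the first year of anastrozole therapy". A footnote to section 3 puts the start of treatment at the first tablet or, failing that, the first prescription.

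**How time is counted.** Section 11.4.1 tabulates arthralgia in intervals that begin with months 0-3 of treatment. It adds: "Time between start of anastrozole therapy and first incidence of arthralgia will be analysed using the Kaplan-Meier method". Time to progression also runs from the start of therapy, by Kaplan-Meier. The same section gives primary interest to the 3-month data, which it explains as data from the first three months of anastrozole therapy. Section 11.3 instead defines the ITT set by data from the first 3 months after study start.

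**Where the window is acknowledged.** A footnote in section 7.1 says that the "12 respectively 15 months observation period results from time slot for inclusion". It draws no consequence for interpretation.

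**The concern.** A woman who stops anastrozole in month 2, for joint pain or any other reason, can never be enrolled. Neither can a woman who stops in month 4 before she has been approached, so the selection reaches up to month 6 for those who enter late. The baseline forms in sections 8.1.2 and 8.2.1 ask back to the start of therapy, but only women who reached enrolment are asked.

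Sections 1.1 and 1.3 describe joint symptoms as limiting compliance and therapy. The women removed before entry are thus plausibly related to both co-primary outcomes. If results are reported as first-year figures from the first tablet, readers will take them as figures for everyone who starts the drug. If early stopping differs between upfront and switch, part of the stratified comparison would come from selection alone.

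**Working it through.** **Planning figures.** Section 11.5 assumes that "compliance will decrease to approximately 50% during the first year of antihormone therapy" and calls a difference of 6 points clinically relevant. For 44% against 50%, two-sided 5%, 80% power and a continuity-corrected chi-square test, the required number is 1119 per group (1086 without the correction). This matches the stated 1119, so the point below is about selection and not about arithmetic.

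**Time points side by side.**
- Enrolment is at month 3 to 6 of therapy.
- The first three months of therapy (section 11.4.1) end at month 3, at or before enrolment for every patient.
- The first three months after study start (section 11.3) run from month 3-6 to month 6-9 of therapy.

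The two descriptions of the 3-month data do not overlap for any patient.

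**Compliance.** Let C be true first-year compliance among all starters and q the share of starters who stop before they can be enrolled. Assume that every early stopper counts as non-compliant. The enrolled cohort then shows C / (1 - q). C = 50% comes from section 11.5; q is an assumption.

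| q | 0.50 / (1 - q) | Overstatement, points |
|---|---|---|
| 2% | 51.0% | 1.0 |
| 5% | 52.6% | 2.6 |
| 10% | 55.6% | 5.6 |
| 15% | 58.8% | 8.8 |
| 20% | 62.5% | 12.5 |

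The overstatement equals 6 points when 0.50 / (1 - q) = 0.56, that is q = 1 - 0.50/0.56 = 10.7%. For C = 44% it is q = 1 - 0.44/0.50 = 12.0%.

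**Upfront against switch.** Take equal true compliance of 50% in both strata, with q = 5% in one and 15% in the other: 58.8% - 52.6% = 6.2 points with no true difference. Shares of 5% against 10% give 2.9 points.

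**Arthralgia incidence.** Let I be true incidence among starters and s the share of early stoppers with arthralgia. The enrolled cohort shows (I - q·s) / (1 - q). For illustration, I = 35.6% (the joint-disorder rate on anastrozole in section 1.1) and q = 10%:
- s = 80%: (0.356 - 0.080)/0.90 = 30.7%
- s = 50%: (0.356 - 0.050)/0.90 = 34.0%
- s = 35.6%: 35.6%, no bias
- s = 20%: (0.356 - 0.020)/0.90 = 37.3%

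The sign depends on whether early stoppers had more or less arthralgia than starters overall.

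**Time to progression.** A woman who progresses before enrolment does not enter the cohort. In a Kaplan-Meier analysis started at the first tablet, enrolled women are counted at risk during 3 to 6 months in which they could not have had the event and still been enrolled.

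**The case against.** The window is disclosed in several places, section 11.1 makes all p-values descriptive-exploratory, and no sentence expressly claims a rate for all starters. Compliance is scored from doctor and patient answers at 0, 3, 6 and 9 months after study start, so it is a repeated percentage among enrolled women, and the protocol does not say how an early stopper would be scored. Early arthralgia is collected retrospectively, so the 0-3 month interval is not empty. All of this is fair. It limits the size of the claim but does not remove the mismatch: the objectives and the time origin refer to the first year from the first tablet, and nothing restricts the conclusions to women who persisted. An analysis plan cannot recover women who left no record.

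Four stronger readings are tempting and are not supported.
- **All results are too favourable.** For arthralgia this needs early stoppers to have had more of it. The protocol makes that plausible, but section 8.1.3 also lists hot flushes, headache, the patient's wish and the physician's recommendation as reasons for stopping.
- **The bias is larger, using 77% compliance.** Section 1.3 reports 23% non-compliant after a year on tamoxifen. From 77%, shares of 5%, 10% and 15% would give 81.1%, 85.6% and 90.6%. But 50% is the protocol's own planning value, and 77% comes from another drug.
- **Discontinuation and death rates are wrongly timed from the first tablet.** No such person-time rates are planned. Section 11.1 counts stops within the study period, and section 11.4.2 gives numbers and percentages of patients.
- **The sample size fails.** A planning value near 50% has the largest variance. If selection raises compliance further above 50%, 1119 per group has more power for 6 points, not less.

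**Conclusion.** The point holds as a mismatch between eligibility and objectives. The enrolled cohort can describe women still on anastrozole 3 to 6 months after starting; it cannot estimate first-year compliance, arthralgia incidence or time to progression for all starters. The time point of primary interest, as section 11.4.1 words it, precedes enrolment and conflicts with section 11.3.

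For compliance the direction is upward provided early stoppers count as non-compliant. On the 50% base the size is 2.6 to 8.8 points for early-stop shares of 5% to 15%, and it passes the 6-point relevant difference at about 10.7%. The documents give no early-stop share, overall or by stratum, so these are scenarios and not estimates. The 6.2-point gap between strata shows what unequal stopping could do; nothing in the protocol shows that stopping is unequal. Understated early arthralgia is probable, not established.

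**What to change.** 1. In sections 3 and 11.4.1, restate the co-primary and incidence objectives as applying to women still taking anastrozole 3 to 6 months after start.
2. Reconcile the primary time point in section 11.4.1 with the period after study start used in section 11.3.
3. Label the 0-3 month arthralgia interval and the time-to-first-arthralgia curve as retrospective and conditional on persistence to enrolment.
4. Analyse time to progression with delayed entry: keep the first tablet as time origin, but let each woman join the risk set only at enrolment.
5. Add one sensitivity table for upfront against switch that re-inserts assumed early stoppers as non-compliant. For each stratum, adjusted compliance = observed compliance × (1 - q), with q from 0% to 15% varied separately by stratum.

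The cost is wording in two sections, a changed risk set in one analysis and one extra table. Eligibility, data collection and sample size stay as they are. The downside is that the study can no longer claim a first-year rate for all starters.
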